9.1.8 Postoperative Follow-Up Visit 7 (12 Months [365 ± 60 days])

- 1. Query subject regarding any changes in general health and the use of concomitant medications. If any AEs, ADEs or DDs are observed or reported, they must be recorded as instructed in Section 12 Adverse Events and Device Deficiencies.
- 2. Complete the Constant-Murley Questionnaire (Physician/Examiner completed portion).
- 3. Have the subject complete the OSS Questionnaire.
- 4. Have the subject complete the WOR/C-WORC Questionnaire.
- 5. Have the subject complete the subjective part of Constant-Murley Questionnaire.
- 6. Have the subject complete the SSV Questionnaire.
- 7. Have the subject complete the EQ-5D-5L Questionnaire.
- 8. Have the subject complete Patient satisfaction Questionnaire.
- 9. Have the subject complete the Return to Work Questionnaire (if appropriate).
- 10. Complete MRI assessment.
- 11. If any Reoperation occurred complete reoperation CRF.
- 12. Complete End of Study/exit information (if appropriate).
- 13. Instruct the subject on follow-up procedures, including returning the treatment facility for follow-up at Visit 8 at 24 months (730 ± 60 days).

9.1.9 Postoperative Follow-Up Visit 8 (24 Months [730 ± 60 days])

- 1. Query subject regarding any changes in general health and the use of concomitant medications. If any AEs, ADEs or DDs are observed or reported, they must be recorded as instructed in Section 12 Adverse Events and Device Deficiencies.
- 2. Complete the Constant-Murley Questionnaire (Physician/Examiner completed portion).
- 3. Have the subject complete the OSS Questionnaire.
- 4. Have the subject complete the WOR/C-WORC Questionnaire.
- 5. Have the subject complete the subjective part of Constant-Murley Questionnaire.
- 6. Have the subject complete the SSV Questionnaire.

CONFIDENTIAL AND PROPRIETARY

Study Protocol	Smith-Nephew
A Prospective, Multi-center, Randomized Controlled	Number:
Study to Evaluate the Safety and Efficacy of ARCR	REGENETEN.2020.01
augmented with REGENETEN™ Bioinductive Implant	Version: 2.0, 08 Dec
System in Full-thickness Tears (large or massive) Repair	2021
versus ARCR alone	Page: 60 of 134

- 7. Have the subject complete the EQ-5D-5L Questionnaire.
- 8. Have the subject complete Patient satisfaction Questionnaire.
- 9. Have the subject complete the Return to Work Questionnaire (if appropriate).
- Complete MRI assessment.
- 11. If any Reoperation occurred complete reoperation CRF.
- 12. Complete Exit Visit CRF and inform subject of End of Study.

9.1.10 Unscheduled Visits

Unscheduled examinations related to the study shoulder may be conducted at the discretion of the Investigator with all obtained information recorded in the source documents. The reason for the unscheduled visit as well as surgical status should be transcribed to the appropriate eCRF. If any adverse events or device deficiencies are observed or reported, they must be recorded as instructed in Section 12. - Adverse Events and Device Deficiencies. The subject should be scheduled to return for the next scheduled study visit within the acceptable time window.

9.1.11 Concomitant Medications and Therapies

Concomitant medications and concomitant therapies (e.g. use of opioids, non-opioid prescription medication, steroid injections to treat the index shoulder) are recorded at any time from enrollment into the study through the subject's last study visit.

9.1.11.1 Concomitant Medications

9.1.11.1.1 Excluded Concomitant Medications

No restrictions on concomitant medications.

CONFIDENTIAL AND PROPRIETARY

Study Protocol	Smith-Nephew
A Prospective, Multi-center, Randomized Controlled	Number:
Study to Evaluate the Safety and Efficacy of ARCR	REGENETEN.2020.01
augmented with REGENETEN™ Bioinductive Implant	Version: 2.0, 08 Dec
System in Full-thickness Tears (large or massive) Repair	2021
versus ARCR alone	Page: 61 of 134

9.1.11.1.2 Recording Concomitant Medication in the eCRF

Only medication related to the study treatment and therapies used to treat an adverse event related to study device and/or study procedure and device deficiency will be recorded in the eCRF according to the eCRF Completion Guidelines.

9.1.11.2 Concomitant Therapies

9.1.11.2.1 Therapies Prohibited During the Study

No restriction on concomitant therapies.

9.1.11.2.2 Recording Concomitant Therapies in the eCRF

Only therapies related to the study treatment and therapies used to treat an adverse event related to study device will be recorded in the eCRF according to the eCRF Completion Guidelines.

9.1.12 Discontinued Subjects

Discontinued subjects are those who voluntarily discontinue participation, who are withdrawn for reasons of safety, who are LTFU, or meet any of the criteria listed in Section 7.8 of this protocol. Where possible, a full Exit Visit should be completed for all subjects who discontinue the study early. Where consent is withdrawn, the date and any reason given for discontinuation should be captured, at a minimum.

Finally, if appropriate, the Investigator will also advise the subject of subsequent therapy and/or procedures necessary for their medical condition.

9.1.13 Subject Pregnancy

Pregnant or breast-feeding females are excluded from the study. If during the course of the study a subject becomes pregnant, study procedures that are contraindicated during pregnancy

CONFIDENTIAL AND PROPRIETARY

Study Protocol	Smith-Nephew
A Prospective, Multi-center, Randomized Controlled	Number:
Study to Evaluate the Safety and Efficacy of ARCR	REGENETEN.2020.01
augmented with REGENETEN™ Bioinductive Implant	Version: 2.0, 08 Dec
System in Full-thickness Tears (large or massive) Repair	2021
versus ARCR alone	Page: 62 of 134

and/or lactation (e.g. X-Rays, MRI) will not be obtained; however, the subject will continue to be followed for study visits and information will be collected regarding the outcome of the birth.

9.2 STUDY METHODS AND MEASUREMENTS

9.2.1 Cofield classification

The Cofield classification system will be used for all MRI analyses to assess the size of FTTs [38]:

- Small = < 1 cm
- Medium = 1-3 cm
- Large = 3-5 cm
- Massive = > 5 cm

9.2.2 OSS Questionnaire

The Oxford Shoulder Score (OSS) is a questionnaire for the assessment of outcomes of shoulder surgery, which can reduce the observer's errors in the evaluation. It contains 12-item patient-reported outcome (PRO) measures specifically designed and developed for assessing outcomes of shoulder surgery such as assessing the impact on patients' quality of life of degenerative conditions (e.g., arthritis and rotator cuff problems). Because of its reliability and effectiveness, this scoring tool is widely used in clinical practice and studies related to shoulder surgery outcomes [39].

The OSS consists of 12 questions each scored 0 to 4 (0=unbearable, 1=severe, 2=moderate, 3=mild, 4=none) with 4 representing the best outcome. When the 12 items are summed, this produces overall scores that run from 0 to 48, with zero (0) representing a severe shoulder problem and 48 representing no related problem. Higher scores represent better clinical outcomes [39]

CONFIDENTIAL AND PROPRIETARY

Study Protocol	Smith-Nephew
A Prospective, Multi-center, Randomized Controlled	Number:
Study to Evaluate the Safety and Efficacy of ARCR	REGENETEN.2020.01
augmented with REGENETEN™ Bioinductive Implant	Version: 2.0, 08 Dec
System in Full-thickness Tears (large or massive) Repair	2021
versus ARCR alone	Page: 63 of 134

A paper questionnaire will be provided by the Sponsor to be completed by the subject. Responses will be recorded in the eCRF.

9.2.3 WORC/C-WORC Index

The WORC/C-WORC Index is a 21-item questionnaire assessing quality of life, evaluating the change in symptoms and functional ability, specific to rotator cuff tendinopathy; it is often used to compare pre- and postoperative changes in patients with a clinical diagnosis of an impingement syndrome, rotator cuff tendinopathy as well as ARCRs [40].

The WORC/C-WORC Index is self-administered, and includes a 5 different domains (physical symptoms, sports and recreation, work, social function, and emotions). Each question uses a visual analog scale (VAS) representing a 100-point scale ranging from 0 to 100. The maximum score is 2100 (worst possible symptoms). Zero (0) represents no symptoms at all. The final score can also be presented as a percentage by subtracting the total from 2100, dividing by 2100, and multiplying by 100. This will give you an overall percentage. The total final WORC/C-WORC Index scores can, therefore, range from 0% (lowest functional status level) to 100% (highest functional status level) [40].

A paper questionnaire will be provided by the Sponsor to be completed by the subject. Responses will be recorded in the eCRF.

9.2.4 Constant-Murley Score

The Constant-Murley Score is a validated assessment of pain and shoulder functionality. The test is divided into four subscales: pain, activities of daily living, strength and range of motion (forward elevation, external rotation, abduction and internal rotation of the shoulder. The subjective findings (severity of pain, activities of daily living and working in different positions) comprise 35 points and the objective (examiner assessed) measurements (arm range of motion

CONFIDENTIAL AND PROPRIETARY

Study Protocol	Smith-Nephew
A Prospective, Multi-center, Randomized Controlled Study to Evaluate the Safety and Efficacy of ARCR	Number: REGENETEN.2020.01
augmented with REGENETEN™ Bioinductive Implant	Version: 2.0, 08 Dec
System in Full-thickness Tears (large or massive) Repair versus ARCR alone	2021 Page: 64 of 134

without pain, measurements of exo- and endorotation via reference points and measuring muscle strength) comprise the remaining 65 points, for a total of 100 points [41].

The Constant Score is divided into 4 subscales: pain (15 points; VAS score range of 0-15), activities of daily living (20 points; range 0=worst, 5=best), strength (25 points; 1 point given per 0.5 kg of weights raised), and range of motion – forward flexion, external rotation, abduction and internal rotation of the shoulder (40 points; range 0=worst, 10=best). The higher the score, the higher the quality of function [41].

A paper questionnaire will be provided by the Sponsor to be completed by the subject. Responses will be recorded in the eCRF.

9.2.5 Subjective Shoulder Value (SSV) (also known as Single Assessment Numeric Evaluation [SANE])

Note: The SANE and the SSV are the same, 'How would you rate your shoulder today as a percentage of normal (0% to 100% scale with 100% being normal)?'

The SSV is defined as a patient's subjective shoulder assessment expressed as a percentage of an entirely normal shoulder, which would score 100% [42].

A paper questionnaire will be provided by the Sponsor to be completed by the subject. Responses will be recorded in the eCRF.

9.2.6 Patient Satisfaction Questionnaire

The Patient Satisfaction Questionnaire is a simple subjective assessment of the success of surgery from the patient's perspective. It has not been formally validated [42].

Pre-Op:

CONFIDENTIAL AND PROPRIETARY

Study Protocol	Smith-Nephew
A Prospective, Multi-center, Randomized Controlled	Number:
Study to Evaluate the Safety and Efficacy of ARCR	REGENETEN.2020.01
augmented with REGENETEN™ Bioinductive Implant	Version: 2.0, 08 Dec
System in Full-thickness Tears (large or massive) Repair	2021
versus ARCR alone	Page: 65 of 134

The Patient satisfaction pre-Op will be documented on a visual analogue score of 0-100 'How satisfied are you with your medical care?' Rated by the subject with 0 is the least satisfied, 100 the most satisfied [43].

Post-Op:

This includes the VAS Patient Satisfaction Score as for pre-Op and additional five questions ask of the patient:

- 1. How well did the surgery relieve the pain?
- 2. How well did the surgery increase your ability to perform regular activities?
- 3. How well did the surgery allow you to perform heavy work or sport activities (if allowed by Dr)?
- 4. How well did the surgery meet your expectations?

Questions rated by the patient with excellent, very good, good, fair and poor.

5. Would you have the operation again if needed on another joint?

Question rated by the patient with Definitely yes, Probably yes, Possibly not, Definitely not [42].

A paper questionnaire will be provided by the Sponsor to be completed by the subject. Responses will be recorded in the eCRF.

9.2.7 VAS Pain Score

Pain is assessed on a 100-point scale ranging from 0 to 100, with zero (0) representing no pain and 100 representing the worst pain imaginable [42].

A paper questionnaire will be provided by the Sponsor to be completed by the subject. Responses will be recorded in the eCRF.

CONFIDENTIAL AND PROPRIETARY

Study Protocol	Smith-Nephew
A Prospective, Multi-center, Randomized Controlled	Number: REGENETEN.2020.01
Study to Evaluate the Safety and Efficacy of ARCR augmented with REGENETEN™ Bioinductive Implant	Version: 2.0, 08 Dec
System in Full-thickness Tears (large or massive) Repair	2021
versus ARCR alone	Page: 66 of 134

9.2.8 Sugaya Score

The Sugaya score will be used to determine postoperative cuff integrity through magnetic resonance imaging classified into 5 categories: Type I to Type V. Type I indicates sufficient thickness with homogenously low intensity. Type II indicates sufficient thickness with partial high intensity. Type III indicates insufficient thickness without discontinuity. Type IV indicates presence of a minor discontinuity, suggesting a small full-thickness tear. Type V indicates the presence of a major discontinuity, suggesting a medium or large full-thickness tear [43]

9.2.9 Goutallier Classification

The Goutallier classification will be used to classify the fatty infiltration of the rotator cuff. The Goutallier classification ranges from a grade of 0 indicating a completely normal muscles without any fatty streaks to a grade of 4 which indicates that more fat than muscle is present [44].

- Grade 0: Completely normal muscle, without any fatty streaks,
- Grade 1: Some fatty streaks,
- Grade 2: Increased fatty infiltration, but more muscle than fat,
- Grade 3: Equal amounts of fat and muscle,
- Grade 4: more fat than muscle.

9.2.10 Return to Work Questionnaire

Generic questionnaire, covering work related questions, including demographics on laborer/sedentary [42].

- Were you working before surgery? Y/N
 - a. If yes, what was your job type and the nature of your work?
- 2. Have you returned to work? Y/N

CONFIDENTIAL AND PROPRIETARY

Study Protocol	Smith-Nephew
A Prospective, Multi-center, Randomized Controlled	Number:
Study to Evaluate the Safety and Efficacy of ARCR	REGENETEN.2020.01
augmented with REGENETEN™ Bioinductive Implant	Version: 2.0, 08 Dec
System in Full-thickness Tears (large or massive) Repair	2021
versus ARCR alone	Page: 67 of 134

- a. If yes, how long after your operation did you return to work
- b. if you couldn't get back to work was there a particular reason?
- 3. Have you been able to return to the job you did before your surgery (doing the same activities)? Y/N
 - a. If No, is there a particular reason you couldn't return to the same activities?
- 4. If RTW, did you feel ready to go back to work physically? Y/N
- 5. Since returning to work, did you have to take further time off due to shoulder pain or weakness? Y/N
 - a. If so, how long?

A paper questionnaire will be provided by the Sponsor to be completed by the subject. Responses will be recorded in the eCRF.

9.2.11 Duration of Opioid Use

Self-reported opioid use diary completed by the patient on a daily basis, from day 0-14, documenting opioid use. Consumption daily (YES/NO) x14 days, 'Have you taken any opioid medication today for shoulder pain?' Y/N.

A paper questionnaire will be provided by the Sponsor to be completed by the subject. Responses will be recorded in the eCRF.

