8.3.2 Secondary Endpoints

The secondary study endpoints are:

- The cumulative 3, 12, and 24 months retear rate after full-thickness ARCR augmented with REGENETEN (confirmed on MRI) versus ARCR alone;
- Overall performance of full-thickness ARCR augmented with REGENETEN versus ARCR alone at Baseline and at 3, 6, 12 and 24 months assessed by:
 - Oxford Shoulder Score (OSS),
 - Western Ontario Rotator Cuff (WORC)/Chinese version WORC (C-WORC) Index,
 - Constant-Murley Score,
 - Subjective shoulder value (SSV),
 - o EuroQol 5 Dimension 5 Level (EQ-5D-5L) Score,
 - Patient satisfaction Questionnaire,
 - Pain, Visual analog scale (VAS) Score (additionally at baseline, 2 weeks, 6 weeks, 3 months and 6 months);
- MRI Tendon Findings in ARCR augmented with REGENETEN versus ARCR alone postoperatively at Baseline, 3, 6, 12 and 24 months including:
 - Sugaya score,

CONFIDENTIAL AND PROPRIETARY

Study Protocol	Smith-Nephew
A Prospective, Multi-center, Randomized Controlled	Number:
Study to Evaluate the Safety and Efficacy of ARCR	REGENETEN.2020.01
augmented with REGENETEN™ Bioinductive Implant	Version: 2, 08 Dec 2021
System in Full-thickness Tears (large or massive) Repair versus ARCR alone	Page: 49 of 134

- Goutallier grading,
- o Total tendon thickness, tendon length,
- Size of retear (anteroposterior [AP]/mediolateral [ML]),
- Shape of retear;
- Outcome of Return to Work Questionnaire in ARCR augmented with REGENETEN versus ARCR alone (additionally at 2 and 6 weeks);
- Cumulative duration of opioid use in ARCR augmented with REGENETEN versus ARCR alone at 2 weeks postoperatively;
- Total operative time in ARCR augmented with REGENETEN versus ARCR alone;
- Sling type and mobilization time in ARCR augmented with REGENETEN versus ARCR alone.

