9. STUDY PROCEDURES

9.1 VISITS AND EXAMINATIONS

9.1.1 Summary

For a summary of the required procedures by visit, refer to the Study Schematic Table 9.1.1-1: Study Procedures by Visit.

CONFIDENTIAL AND PROPRIETARY

Study Protocol	Smith
----------------	-------

A Prospective, Multi-center, Randomized Controlled Study to Evaluate the Safety and Efficacy of ARCR augmented with REGENETEN™ Bioinductive Implant System in Full-thickness Tears (large or massive) Repair versus ARCR alone

Number: REGE Version: 2.0, 08 Dec 2021

Page: 54 of 134

Table 9.1.1-1: Study Procedures by Visit

Schedule of Event	Screening (Baseline) Day -60 to Day -1	Operation Day 0	2 Weeks Follow- up 14 ± 5 Days	6 Weeks Follow- up 42 ± 7 Days	3 Months Follow- up 91 ± 15 Days	6 Months Follow- up 182 ± 30 Days	N F uj
Informed Consent	X ¹						
Inclusion/Exclusion	X ²	X ²					
Demographics/Medical History/BMI	Х						
Operative/Discharge Data		X					
Oxford Shoulder Score	X				X	X	
WORC/C-WORC	X				X	Х	
Constant-Murley Score	X				X	X	
Subjective Shoulder Value	X				X	X	
EQ-5D-5L	X				X	X	
Patient Satisfaction	X				X	X	
VAS Pain Score	X		X	X	X	X	
Return to Work Questionnaire	X		X ³	X ³	X ³	X ³	
Opioid Use			X ⁴				
Reoperation			X	X	X	X	
MRI Assessment	X ²				X	Х	
Concomitant Medication/Therapy	Х	Х	Х	Х	Х	Х	
Safety Assessment (AEs, DDs)		X	Х	X	Х	X	
End of Study/Exit		X ³	X ³	X ³	X ³	X ³	

¹ Date of Informed consent may be the same day or another day before screening giving the subject enough time to consider particip ² Inclusion/exclusion confirmation will be performed at the time of screening and study procedure to confirm subject meets eligibility c be confirmed on arthroscopy using a calibrated probe. X-Ray and MRI to confirm eligibility criteria must be within 12 months of surge ³ As appropriate.

CONFIDENTIAL AND PROPRIETARY

This document contains information that is confidential and proprietary to Smith+Nephew PLC and Smith+Nephew, Inc. and is intended for use only manufacturer. It shall not be reproduced or copied in whole or in part, nor shall the contents be disclosed by any means without prior written permiss nor shall anyone make any use of it that is contrary to the expressed or implied wishes of Smith+Nephew.

TMP-CD-05-01 - Clinical Protocol-Device - Revision D.1; SOP-CD-05 Clinical Protocols

⁴ Opioid use will be documented daily from day 0 to day 14.

Study Protocol	Smith-Nephew
A Prospective, Multi-center, Randomized Controlled	Number:

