9.1.3 Operation – Visit 2 (Day 0)

- 1. Query subject regarding any changes in general health and the use of concomitant medications (e.g. oral or injected steroid use in last 4 weeks).
- 2. Confirm eligibility based on arthroscopic visualization of the tear and confirm size using a calibrated probe.
- 3. Assign the Randomization ID per randomization schedule. Screen Failure subjects should not be assigned randomization numbers, but their demographic information must be captured in the appropriate CRF with the reason for screen failure specified.
- 4. Commence operation as per the randomization schedule.
- 5. Collect operative and discharge data (including implant information) according to the CRF.
- 6. If any AEs, ADEs or DD are observed or reported, they must be recorded as instructed in Section 12 Adverse Events and Device Deficiencies.
- 7. Instruct the subject on proper postoperative care/procedures as per standard of care and/or Sponsor's recommendation given in section 6.2 Product Use.
- 8. Instruct the subject to document Opioid Use over the next 2 weeks on a daily basis.
- 9. Instruct the subject on follow-up procedures, including returning the treatment facility for follow-up at Visit 3 in 14 (± 5) days.

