9.1.4 Postoperative Follow-up Visit 3 (2 Weeks [14 days ± 5 days])

- Query subject regarding any changes in general health and the use of concomitant medications. If any AEs, ADEs or DDs are observed or reported, they must be recorded as instructed in Section 12 – Adverse Events and Device Deficiencies.
- 2. Have the subject complete VAS pain score.
- 3. Have the subject complete the Return to Work Questionnaire (if appropriate).

CONFIDENTIAL AND PROPRIETARY

Study Protocol	Smith-Nephew
A Prospective, Multi-center, Randomized Controlled	Number:
Study to Evaluate the Safety and Efficacy of ARCR	REGENETEN.2020.01
augmented with REGENETEN™ Bioinductive Implant	Version: 2.0, 08 Dec
System in Full-thickness Tears (large or massive) Repair	2021
versus ARCR alone	Page: 57 of 134

- 4. Collect daily Opioid Use documentation from subject and enter into eCRF.
- 5. If any Reoperation occurred complete reoperation CRF.
- 6. Complete End of Study/exit information (if appropriate).
- 7. Instruct the subject on follow-up procedures, including returning the treatment facility for follow-up at Visit 4 at 42 (± 7) days.

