10.4.2 Analysis of Secondary Endpoints

The following secondary endpoints will be analyzed for this study:

- Retear rate at 3, 12 and 24 months post-operative will be summarized and presented as per the Primary Endpoint analysis.
- OSS, WORC/C-WORC, Constant, SSV and EQ-5D-5L PRO scores will be calculated and summarized for each visit using descriptive statistics for continuous variables, separately for the ARCR augmented with REGENETEN group and the ARCR alone (standard of care) group. Changes from baseline to each subsequent follow up visit will be similarly summarized. Repeated measures ANCOVA models will be used to assess statistical significance in the change from baseline to each time point. The null hypothesis will be that there is no difference between baseline and the respective time point. An estimate of the LS mean difference between the time points for the scores will be reported, along with the corresponding 95% confidence interval and p-value. A separate model will be used to assess statistical significance between the treatment groups at each time point. Minimal Clinically Important Differences will be assessed and presented where appropriate.
- Patient satisfaction and return to work questionnaire will be presented as number and percentage of patients who have selected each of the responses at each time point. The duration a patient has taken away from work will be summarized descriptively.
- VAS Pain score (1-100mm) will be summarized at baseline, 2 and 6 weeks, 3, 6, 12 and 24 months using descriptive statistics for continuous variables. Change from baseline to each follow up assessment will be similarly summarized and p-values will be presented.

CONFIDENTIAL AND PROPRIETARY

Study Protocol	Smith-Nephew
A Prospective, Multi-center, Randomized Controlled	Number:
Study to Evaluate the Safety and Efficacy of ARCR	REGENETEN.2020.01
augmented with REGENETEN™ Bioinductive Implant	Version: 2.0, 08 Dec
System in Full-thickness Tears (large or massive) Repair	2021
	Page: 73 of 134

- MRI analysis will be conducted by an external vendor at baseline, 3, 6, 12 and 24 months and will be presented appropriately for continuous or categorical variables.
- Opioid use will be collected each day for 2 weeks following surgery. The number of days
 of opioid use will be calculated for each patient and this will be presented descriptively for
 all patients, by treatment type (ARCR augmented with REGENETEN or ARCR alone).

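### The opioid diary is collected at a visit allowed from day 9 with no later retrieval, so the day count can be cut short for continuing users seen early; separately, its length is given as both 15 and 14 days

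*Combined protocol and SAP*

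**What the plan says.** Section 8.3.2 lists the secondary endpoint: "Cumulative duration of opioid use in ARCR augmented with REGENETEN versus ARCR alone at 2 weeks" after surgery.

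The diary period appears in four places:

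- Section 9.2.11: "Self-reported opioid use diary completed by the patient on a daily basis, from day 0-14, documenting opioid use". The next sentence gives "Consumption daily (YES/NO) x14 days". The form is a sponsor-supplied paper questionnaire transcribed to the eCRF.
- Footnote 4 of the visit schedule (Synopsis and Table 9.1.1-1): "Opioid use will be documented daily from day 0 to day 14".
- Section 9.1.3, at the operation visit: "Instruct the subject to document Opioid Use over the next 2 weeks on a daily basis".
- Section 10.4.2: "Opioid use will be collected each day for 2 weeks following surgery".

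Collection appears once, as a step of Visit 3 in Section 9.1.4: "Collect daily Opioid Use documentation from subject and enter into eCRF". That visit is allowed at 14 ± 5 days. The only opioid mark in the schedule as supplied is in the 2-week column, and the procedure lists for Visits 4 to 8 (Sections 9.1.5 to 9.1.9) do not mention the diary.

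For analysis, Section 10.4.2 counts days of use for each patient and presents the count descriptively by treatment. It gives no denominator and no rule for missing days.

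**The concern.** The diary is defined by a fixed period, but the step that collects it is tied to a visit that may come up to five days before that period ends. A site following Section 9.1.4 literally on day 9 takes the paper diary, enters what is there, and is never told to obtain the rest. Because the outcome is a plain count, an entry that was never collected looks the same as a day without opioids.

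The loss falls only on subjects still using opioids late in the window, so it compresses the upper end of the distribution, which is where a duration measure carries its information. Visit timing then becomes part of the measurement. The study is not blinded (Section 8.2.2), and nothing in the plan ensures equal visit timing in the two arms.

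The second matter is separate. A reader cannot tell whether the maximum score is 14 or 15, or which end day would be dropped.

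**Working it through.** **Diary length.** The stated figure is 14 entries (Section 9.2.11).

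- Day 0 to day 14 inclusive: 14 − 0 + 1 = 15. This does not reproduce 14.
- Day 1 to day 14: 14 entries.
- Day 0 to day 13: 14 entries.

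So 14 is reached only by dropping one end day, and the text does not say which. The difference is 1/15 = 7% of the maximum.

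**Visit window.** 14 − 5 = day 9 and 14 + 5 = day 19, which gives 11 permitted days.

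**Entries in hand at collection.** Assume the diary closes at the visit. For a visit on day v, the number of entries is min(v, 14) + 1 if the visit-day entry has been made, and min(v − 1, 14) + 1 if not.

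| Visit day | Entries, visit day included | Lost of 15 | Entries, visit day not included | Lost of 15 |
|---|---|---|---|---|
| 9 | 10 | 5 | 9 | 6 |
| 10 | 11 | 4 | 10 | 5 |
| 11 | 12 | 3 | 11 | 4 |
| 12 | 13 | 2 | 12 | 3 |
| 13 | 14 | 1 | 13 | 2 |
| 14 | 15 | 0 | 14 | 1 |
| 15–19 | 15 | 0 | 15 | 0 |

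Five of the 11 permitted days (9 to 13) can shorten the record, or six if the day-14 entry is not made before collection. The maximum loss is 5/15 = 33%, or 6/15 = 40%. If the intended window is day 1 to day 14, the same 5 or 6 entries are lost, out of 14.

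**Who is affected.** A subject loses counted days only if opioids are used on an uncollected day. Someone whose last day of use is day 8 or earlier has every day of use recorded even at a day-9 visit without the visit-day entry.

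**Average effect, as an illustration.** The documents give neither the distribution of visit dates nor the pattern of use. Assume visits spread evenly over days 9 to 19 and unbroken use from day 0.

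- 15-day user, visit-day entry made: (10 + 11 + 12 + 13 + 14 + 6 × 15)/11 = 150/11 = 13.6 days, a loss of about 9%.
- 15-day user, visit-day entry not made: (9 + 10 + 11 + 12 + 13 + 14 + 5 × 15)/11 = 144/11 = 13.1 days, a loss of about 13%.
- 12-day user: (10 + 11 + 9 × 12)/11 = 129/11 = 11.7 days, or (9 + 10 + 11 + 8 × 12)/11 = 126/11 = 11.5 days.
- User of 7 days or fewer: no loss.

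**The case against.** The strongest reply is that no passage says the diary ends at Visit 3. Every statement of the period fixes it without reference to the visit, so a sensible site would let the subject finish. That stands as far as intent goes: a reader might infer that the endpoint is truncated by visit timing as a matter of design, and the documents do not support this. They leave it open. What remains is that the only stated collection step can come before the stated period ends, and nothing says how the remaining days reach the eCRF.

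Section 10 calls itself a brief description of a SAP to be finalised before database lock, so missing-day rules may follow there. A SAP can define the window and the handling of gaps, but it cannot recover entries that were never collected.

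Section 9.1.11 names opioids among the concomitant medications recorded through the last visit. That record is not linked to this endpoint, and nothing requires it to hold daily yes/no data.

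The consequence is small. The endpoint is one of many secondary ones, is presented descriptively, and has no specified test or power. This stands in full.

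Two further inferences are tempting and should not be drawn. One is that subjects in pain attend early, so that the longest users are the ones cut short. Visit 3 is a scheduled return, Section 9.1.10 provides separately for unscheduled examinations, and no data on attendance are given. The other is that the 14/15 mismatch contributes to the truncation. It does not; it is a one-day ambiguity that would exist whatever the visit date.

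**Conclusion.** The concern holds in a limited form. For subjects seen on days 9 to 13, or on day 14 before that day's entry is made, who are still taking opioids and whose later entries are not retrieved, the count can be short by up to 5 of 15 days (6 without the visit-day entry). That maximum needs a visit on the first permitted day and use on every lost day. Under evenly spread visits, which is an assumption, a continuous 15-day user would lose about 1.4 to 1.9 days on average.

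Bias between arms would need visit timing, late opioid use or retrieval of late entries to differ by arm. The documents show none of these, so it is a risk and no more. The two diary lengths are a separate inconsistency that must be reconciled. Neither matter touches the primary endpoint or the sample size. This is a minor point, worth making because the remedy is nearly free and works only while diaries are still being collected.

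**What to change.** 1. State one fixed diary window, with its first and last day and the number of entries, in the same terms in Section 9.2.11, footnote 4 (both schedules) and Section 10.4.2.
2. Add to Section 9.1.4 that a diary incomplete at Visit 3 is continued to its last day, and that the remaining days are returned at the next contact or at Visit 4.
3. Report the number of diary days observed by arm beside the days of use, so that any residual shortfall is visible.

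Modelling days of use with the log of days observed as an offset is not recommended as the analysis. It assumes the same daily rate of use on unobserved days. If use declines over the two weeks (again an assumption), a diary cut at day 9 covers the heavier period and the offset would overstate that subject's use. Retrieving the pages removes most of the need for it.

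The cost is a few sentences of protocol and SAP text and a few diary pages returned later.
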